**Additional Note:**

Summaries of amenorrhea are based upon the sub-population of patients who are at risk of this AE, including women of child-bearing potential or having menses at baseline. The demography CRF page captures whether patients are of child-bearing potential but there is nowhere to indicate whether patients have menses, and so all patients who experienced the AE of interest (Amenorrhea/ Irregular Menses) were also included in the denominator.

Overall summary of AEs:

STREAM Template	Description
AET01	Output ID: t_ae_o_* 

● Analysis Population: Safety

● Column Variables: Disease Status (Locally Advanced, Metastatic)

● Column Totals: Totals of non-missing Disease Status

● Analysis Variables: Total Patients with at least one AE, Total number of events, Total number of deaths, Total number of patients withdrawn from study due to an AE, Total number of patients with at least one: AE with Fatal outcome, Serious AE, Serious AE leading to treatment withdrawal, Serious AE leading to dose modification/interruption, AE leading to treatment withdrawal, AE leading to dose modification/interruption

● Numeric Precision and Formatting of Statistics: Use standard display in the mockup

Number of patients reporting AEs:

STREAM Template	Description
AET02	
Output ID: t_ae_*
 

● Analysis Populations: Safety Output will be repeated for different population combinations - please see the LoPO for details of these combinations

● Column Variables: Disease Status (Locally Advanced, Metastatic)

● Column Totals: Totals of non-missing Disease Status

● Analysis Variables: MedDRA System Organ Class, MedDRA Preferred Term.

● Statistics and Calculation Methods: Use proq freq for events or proc sql for patient counts.

● Numeric Precision and Formatting of Statistics: Use standard display in the mockup

● Optional Subsetting: For each System Organ Class and Preferred Term, include Total number of patients with at least one AE, Overall total number of events

Number of patients reporting AEs by Sub-group:

STREAM Template	Description
AET02	
Output ID: t_ae_bysubgp_*
 
 
● Analysis Populations: Safety
 
● Column Variables: Disease Status (Locally Advanced, Metastatic)
 
● Column Totals: Totals of non-missing Disease Status
 
● Analysis Variables: MedDRA System Organ Class, MedDRA Preferred Term.
 
● Statistics and Calculation Methods: Use proq freq for events or proc sql for patient counts.
 
● Numeric Precision and Formatting of Statistics: Use standard display in the mockup
 
● Optional Subsetting: For each System Organ Class and Preferred Term, include sub-grouping for: 
 
○ Age (see General Considerations) i.e. <65, >= 65, <75, >= 75.
 
○ Race where Race is taken from the CRF and grouped i.e. White, Non-White, Missing.
 
○ Sex where sex is taken from CRF i.e. Male, Female.
 
○ Baseline (see General Considerations) ECOG Score i.e. 0, 1, >=2, Missing
 
 
 

Number of patients reporting AEs by Severity:

STREAM Template	Description
AET02	
Output ID: t_ae_bysev_*
 
 
● Analysis Populations: Safety Output will be repeated for different population combinations - please see the LoPO for details of these combinations
   
● Column Variables: Disease Status (Locally Advanced, Metastatic)
   
● Column Totals: Totals of non-missing Disease Status
   
● Analysis Variables: MedDRA System Organ Class, MedDRA Preferred Term.
   
● Statistics and Calculation Methods: Use proq freq for events or proc sql for patient counts.
   
● Numeric Precision and Formatting of Statistics: Use standard display in the mockup
   
● Optional Subsetting: For each System Organ Class and Preferred Term, include sub-grouping for: 
 
○ Any Grade
 
○ Grades 1 through 5
 
○ Missing Grade
 
 
 

Number of patients reporting AEs by Drug Relationship:

STREAM Template	Description
AET02	
Output ID: t_ae_byrel_*
 
 
● Analysis Populations: Safety
 
● Column Variables: Disease Status (Locally Advanced, Metastatic)
 
● Column Totals: Totals of non-missing Disease Status
 
● Analysis Variables: MedDRA System Organ Class, MedDRA Preferred Term.
 
● Statistics and Calculation Methods: Use proq freq for events or proc sql for patient counts.
 
● Numeric Precision and Formatting of Statistics: Use standard display in the mockup
 
● Optional Subsetting: For each System Organ Class and Preferred Term, include sub-grouping for: 
 
○ Related
 
○ Not Related
 
○ Not Applicable
 
 
 

Number of patients reporting AEs by Exposure Duration:

STREAM Template	Description
AET02	
Output ID: t_ae_byexp_*
 
 
● Analysis Populations: Safety Output will be repeated for different population combinations - please see the LoPO for details of these combinations
   
● Column Variables: Disease Status (Locally Advanced, Metastatic)
   
● Column Totals: Totals of non-missing Disease Status
   
● Analysis Variables: MedDRA System Organ Class, MedDRA Preferred Term
   
● Statistics and Calculation Methods: Use proq freq for events or proc sql for patient counts.
   
● Numeric Precision and Formatting of Statistics: Use standard display in the mockup
   
● Optional Subsetting: For each System Organ Class and Preferred Term, include sub-grouping for: 
 
○ < 12 months exposure
 
○ >= 12 months exposure
 
 
 

Number of patients reporting AEs by Outcome:

STREAM Template	Description
AET02	
Output ID: t_ae_byout_*
 
 
● Analysis Populations: Safety Output will be repeated for different population combinations - please see the LoPO for details of these combinations
   
● Column Variables: Disease Status (Locally Advanced, Metastatic)
   
● Column Totals: Totals of non-missing Disease Status
   
● Analysis Variables: MedDRA System Organ Class, MedDRA Preferred Term.
   
● Statistics and Calculation Methods: Use proc freq for events or proc sql for patient counts.
   
● Numeric Precision and Formatting of Statistics: Use standard display in the mockup
   
● Optional Subsetting: For each System Organ Class and Preferred Term, include sub-grouping for: 
 
○ Recovered / Resolved
 
○ Not Recovered / Not Resolved
 
○ Recovered / Resolved with SequelAE
 
○ Fatal
 
 
 

Resolution of Collapsed AEs Ongoing by Outcome:

STREAM Template	Description
AET02	
Output ID: t_ae_out_c_*
 
 
● Analysis Populations: Safety Output will be repeated for different population combinations - please see the LoPO for details of these combinations
   
● Column Variables: Disease Status (Locally Advanced, Metastatic)
   
● Column Totals: Totals of non-missing Disease Status
   
● Analysis Variables: MedDRA System Organ Class, MedDRA Preferred Term.
   
● Statistics and Calculation Methods: Use proc freq for events or proc sql for patient counts.
   
● Numeric Precision and Formatting of Statistics: Use standard display in the mockup
   
● Optional Subsetting: For each System Organ Class and Preferred Term, include sub-grouping for: 
 
○ Resolved
 
○ Resolved with SequelAE
 
○ Ongoing
 
○ Fatal
 
○ Unknown
 
○ Missing
 
 
 

Summary of Muscle Spasm AEs Ongoing at the Time of Discontinuation (Collapsed AEs), and Still Ongoing at Last Assessment by Preferred Term, Excluding Patients with Commercial Vismodegib


AET02
	
Output ID: t_ae_out_ongo_AEMUS_*
 
 
● Analysis Population: Safety-Evaluable Patients, 12 Months FU Complete Subset
 
● Column Variables: Disease status (Locally Advanced, Metastatic)
 
● Column Totals: Total of non-missing Disease status
 
● Analysis Variables: MedDRA System Organ Class, MedDRA Preferred Term.
 
● Numeric Precision and Formatting of Statistics: Use standard display in the mockup
 
● Optional Subsetting: For each System Organ Class and Preferred Term, include sub-grouping for:             
 
○ Resolved
 
○ Resolved with SequelAE
 
○ Ongoing
 
○ Fatal
 
○ Unknown
 
○ Missing
 
 
 

---------------------	--

Programming Notes:

- Only ongoing "Muscle Spasm" Adverse Events at the time of discontinuation are included.
- Patients, who took commercial Vismodegib (according to the Concomitant Medication CRF page) between treatment discontinuation and 12 months after treatment and had ongoing Adverse Events at treatment discontinuation, have been excluded.

Summary of Alopecia AEs Ongoing at the Time of Discontinuation (Collapsed AEs), and Still Ongoing at Last Assessment by Preferred Term, Excluding Patients with Commercial Vismodegib

Output Id : t\_ae\_out\_ongo\_AEAL\_\*

Repeat output t\_ae\_out\_ongo\_AEMUS\_\* for “Alopecia” adverse event.

Summary of Ageusia AEs Ongoing at the Time of Discontinuation (Collapsed AEs), and Still Ongoing at Last Assessment by Preferred Term, Excluding Patients with Commercial Vismodegib

Output Id : t\_ae\_out\_ongo\_AEAG\_\*

Repeat output t\_ae\_out\_ongo\_AEMUS\_\* for “Ageusia” adverse event.

Summary of Dysgeusia AEs Ongoing at the Time of Discontinuation (Collapsed AEs), and Still Ongoing at Last Assessment by Preferred Term, Excluding Patients with Commercial Vismodegib

Output Id : t\_ae\_out\_ongo\_AEDY\_\*

Repeat output t\_ae\_out\_ongo\_AEMUS\_\* for “Dysgeusia” adverse event.

Summary of Weight Decreased AEs Ongoing at the Time of Discontinuation (Collapsed AEs), and Still Ongoing at Last Assessment by Preferred Term, Excluding Patients with Commercial Vismodegib

Output Id : t\_ae\_out\_ongo\_AEWG\_\*

Repeat output t\_ae\_out\_ongo\_AEMUS\_\* for “Weight Decreased” adverse event.

Number of Patients reporting TEAEs (Enrolled Population):

STREAM Template	Description
AET02	
Output ID: t_ae2_*
 
 
● Analysis Populations: Enrolled Population Output will be repeated for different population combinations - please see the LoPO for details of these combinations
   
● Column Variables: Disease Status (Locally Advanced, Metastatic)
   
● Column Totals: Totals of non-missing Disease Status
   
● Analysis Variables: MedDRA System Organ Class, MedDRA Preferred Term.
   
● Statistics and Calculation Methods: Use proq freq for events or proc sql for patient counts.
   
● Numeric Precision and Formatting of Statistics: Use standard display in the mockup
   
● Optional Subsetting: For each System Organ Class and Preferred Term, include Total number of patients with at least one AE, Overall total number of events
 

Programming Notes:

- Table to be repeated for TEAEs leading to Death, Serious TEAEs, TEAEs of Grades 3 to 5 and TEAEs Leading to Study Drug Discontinuation.

- Rate of AEs per 100 Patient Years by Exposure Duration:

STREAM Template	Description
AET02	
Output ID: t_ae_byptyr_*
 
 
• Analysis Populations: Safety Output will be repeated for different population combinations - please see the LoPO for details of these combinations
 
• Column Variables: Exposure Duration Categories (< 12 Months Exposure, >= 12 Months Exposure)
 
• Column Totals: None
 
• Analysis Variables: MedDRA System Organ Class, MedDRA Preferred Term.
 
• Numeric Precision and Formatting of Statistics: Use standard display in the mockup
 
• Optional Subsetting: For each System Organ Class and Preferred Term, include Total number of patients with at least one AE, Overall total number of events
 

Disposition of patients with an AE ongoing at treatment discontinuation:

STREAM Template	Description
N/A	
Output ID: t_ae_ds_persae_*
 
 
● Analysis Populations: Safety Output will be repeated for different population combinations - please see the LoPO for details of these combinations
   
● Column Variables: Disease Status (Locally Advanced, Metastatic)
   
● Column Totals: Totals of non-missing Disease Status
   
● Analysis Variables: Total number of Patients with an Ongoing AE at discontinuation, Reason for Discontinuation from Treatment, Patient Died after Discontinuation from Treatment, Patient was Lost to Follow-Up After Discontinuation from Treatment, Latest Protocol Version Consented to
   
● Statistics and Calculation Methods: Use proq freq for events or proc sql for patient counts.
   
● Numeric Precision and Formatting of Statistics: Use AET02 standard template in the mockup
   
● Optional Subsetting: Reason for Discontinuation i.e. Death, Lost To Follow-Up. Patient Died After Discontinuation from Treatment i.e. 0-3 months, 0-6 months, >6 months after discontinuation.
 

Summary of Disposition of Patients with an AE ongoing at the time of Discontinuation (Latest Protocol Version consented to: 1 or 2) (Safety Population)

	Locally Advanced (N=282)	Metastatic (N=16)	Total (N=298)
Total number of patients with an ongoing AE at discontinuation	110 (39.0%)	12 (75.0%)	122 (40.9%)
Reason for Discontinuation from Treatment			
n	5 ( 1.8%)	1 ( 6.3%)	6 ( 2.0%)
Death	4 ( 1.4%)	1 ( 6.3%)	5 ( 1.7%)
Lost To Follow-Up	1 ( 0.4%)	0	1 ( 0.3%)
Patient Died After Discontinuation from Treatment			
n	4 ( 1.4%)	0	4 ( 1.3%)
0-3 months after discontinuation	3 ( 1.1%)	0	3 ( 1.0%)
0-6 months after discontinuation	1 ( 0.4%)	0	1 ( 0.3%)
Patient was Lost to Follow-Up After Discontinuation from Treatment			
n	12 ( 4.3%)	5 (31.3%)	17 ( 5.7%)
0-3 months after discontinuation	12 ( 4.3%)	5 (31.3%)	17 ( 5.7%)
Date of Treatment Discontinuation < 3 Months Before 6th November 2013			
n	6 ( 2.1%)	0	6 ( 2.0%)
Patients	6 ( 2.1%)	0	6 ( 2.0%)
Protocol Version Consented (Latest)			
n	110 (39.0%)	12 (75.0%)	122 (40.9%)
Version 1	21 ( 7.4%)	3 (18.8%)	24 ( 8.1%)
Version 2	89 (31.6%)	9 (56.3%)	98 (32.9%)

Programming Notes:

- Only include the AEs which were ongoing at the time of treatment discontinuation.

Number of Patients Reporting AEs by age group:

STREAM Template	Description
AET02	
Output ID: t_ae_byagegp_*
 
 
● Analysis Populations: Safety Output will be repeated for different population combinations - please see the LoPO for details of these combinations
   
● Column Variables: Age Groups (< 65 and >= 65, < 75 and >= 75)
   
● Column Totals: None
   
● Analysis Variables: MedDRA System Organ Class, MedDRA Preferred Term.
   
● Statistics and Calculation Methods: Use proq freq for events or proc sql for patient counts.
   
● Numeric Precision and Formatting of Statistics: Use AET02 as standard display but with above columns
   
● Optional Subsetting: For each System Organ Class and Preferred Term, include Total number of patients with at least one AE, Overall total number of events
 

Listing of Ongoing Adverse Events for Patients who Discontinued Treatment (Latest Protocol Version Consented to: 1 or 2)

AEL02
	
Output ID: l_ae_ds_PV1N2_AEPERS*
 
 
● Analysis Population: Safety-Evaluable Patients
 
● Column Variables: Disease status (Locally Advanced, Metastatic), Center/Patient ID - Age/Sex/Race, MedDRA Preferred Term, Date of First/ Last Study Drug Admin., Date of Adverse Event, Date of Treatment Disc., Date of Last Known Alive, Reason for Treatment Disc., Related to Study Drug, Serious
 
● Column Totals: NA
 
● Analysis Variables: None
 
● Numeric Precision and Formatting of Statistics: Use standard display in the mockup
 

---------------------	---

Programming notes:

1. Listing includes patients who had an AE ongoing at time of treatment discontinuation, and still ongoing at the time of analysis and patients who latest consented to protocol version 1 and 2.
2. Patients who died or were lost to follow-up within 6 months after treatment discontinuation are excluded.

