Record Date of Last Menses ¹¹	X	X	X	X	X	X	X	X	X	X	X
Pregnancy Test ¹²	X	X	X	X	X	X	X	X	X	X	
Serum Hormone Evaluation ¹³	X	As clinically indicated								As clinically indicated	As clinically indicated
Steady-state and post-treatment pharmacokinetic collection of blood (AT SELECTED SITES ONLY) ²⁴		One collection while taking vismodegib for at least 2 weeks continuously									At 3, 6, 9, and 12 Months ONLY
QoL Assessments using Skindex-16 (in selected sites)	X		X					X		X	

Table 1 Schedule of Assessments (cont.)

Cycle	Screening / Baseline	Treatment Phase ¹ (Allowed Visit Window +/- 3 days from Cycle 2 onwards)								End of Treatment Visit ²	Safety Follow-Up Visits ³ (1 month, 3 months, 6 months, 9 months, 12 months after the last dose of vismodegib (GDC-0499))
		1	2	3	4	5	6	7	8 onwards		
Day	-28 to -1	1	29	57	85	113	141	169	Every 28 Days		
Symptom Assessment using MDASI ¹⁴	X	X	X	X	X	X	X	X	X	X	X
Tumor Assessments (physical examination) ^{15, 17}	X	Every 4 to 8 weeks from the time of the first dose (±5 days) regardless of dosing delays.								X	
Tumor Assessments (by imaging techniques, if required) ^{16, 17}	X	Every 8 to 16 weeks from the time of the first dose (±5 days) regardless of dosing delays or as per institutional standards In metastatic BCC patients (newly enrolled after approval of the Study Protocol, version 4.0), every 8 weeks from time of first dose (±5 days) regardless of dosing delay								X	
AEs / SAEs ¹⁸	X	X								X	X
AE-related pharmacokinetic collection of blood (AT SELECTED SITES ONLY) ²⁵											At 6, 9, and 12 Months ONLY
Ultrasound ¹⁹	X	As clinically indicated								As clinically indicated	As clinically indicated
Follow-up for disease progression		X								X	X
Tumor biopsy and collection of whole blood ²⁰										X	
Concomitant medication	X ²¹	X								X	X
New anti-cancer therapy										X	X
Drug Dispensing		X (first day of each Cycle)									
Drug Accountability ²² Drug Dosing Exception Diary ²³			X	X	X	X	X	X	X	X	X

Table 1 Schedule of Assessments (cont.)

Notes Results of screening tests or examination performed as standard of care before obtaining informed consent and within the specified interval may be used rather than repeating required evaluation. Day 1 = first dose of study drug vismodegib.

1. Visits during the treatment period are to be completed on Day 1 of every 28-Day Cycle.
2. End of Treatment Visit will be performed when the patient discontinues vismodegib regardless of when it occurs.

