3. Safety Follow-Up Visit is to be performed approximately (+/- 5 days) 1 month, 3 months, 6 months, 9 months, and 12 months after the last dose of vismodegib.
4. Written, signed informed consent must be obtained prior to perform any study procedure including screening/baseline assessments.
5. Archival tumor tissue from a metastatic BCC site will be collected in metastatic BCC patients (who are on study after approval of the Study Protocol, version 4.0).
6. In women of childbearing potential, also record any amenorrhea/irregular menses, relevant gynecologic medical history, and concurrent gynecologic conditions. In metastatic BCC patients who are on study after approval of Study Protocol, version 4.0, record evidence of disease progression prior to enrollment on study and reasons for treatment discontinuation of any prior metastatic BCC therapy.
7. A limited physical examination should focus on organ systems that are related to a potential AE as suggested by a patient's interim medical history and/or existing clinical and preclinical data for vismodegib.
8. Height is only measured at screening.
9. Includes body temperature, blood pressure, and pulse.
10. Hematology and biochemistry assessments do not need to be repeated on Day 1 if performed within 7 days of first vismodegib administration. NB: if it is necessary to repeat these blood tests, the results must be known before the patient receives first dose of vismodegib (to ensure inclusion/exclusion criteria related to these tests are met).
11. In women of childbearing potential ONLY.
12. For women of childbearing potential, including those who have had a tubal ligation. A serum pregnancy test is required within 7 days prior to first dose of vismodegib and urine pregnancy tests should be performed on Day 1 of each subsequent Cycle. If a urine pregnancy test is positive, it must be confirmed by a serum pregnancy test.
13. For women of childbearing potential ONLY. To be performed at local laboratory. Includes FSH, TSH, LH and E2. Perform at Screening and at start of amenorrhea/irregular menses and at resolution of amenorrhea/irregular menses. If amenorrhea/irregular menses recurs, repeat evaluations at start of recurrence as detailed previously.
14. M.D. Anderson Symptom Inventory (MDASI) will be completed by metastatic BCC patients (newly enrolled after approval of Study Protocol, version 4.0), prior to having any assessments performed at each visit.

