Female patients who meet at least one of the following criteria are defined as women of non-childbearing potential:

- ≥ 50 years old and naturally amenorrheic for ≥ 1 year
- Permanent premature ovarian failure confirmed by specialist gynecologist
- Previous bilateral salpingo-oophorectomy or hysterectomy
- XY karyotype, Turner's syndrome, or uterine agenesis

Female patients who do not meet at least one of the above criteria are defined as women of childbearing potential.

Additionally, the parent or guardian of young female patients who have not yet started menstruation should verify that menstruation has not begun. If a young female patient reaches menarche during the study, she is to be treated as a woman of childbearing potential from that time forward.

Acceptable contraception

Women of childbearing potential are required to use two forms of acceptable contraception (including one barrier method) during participation in the study and for 9 months or as per approved local prescribing information for vismodegib (where available), whichever is longer, following discontinuation of vismodegib. Acceptable contraception and duration of contraceptive use should comply with locally approved vismodegib (Erivedge[®], the trade name for vismodegib) Pregnancy Prevention Program or prescribing information where vismodegib is commercially available.

Acceptable forms of barrier contraception include the following:

- Latex, non-latex, or any other male condom (always used with spermicide [*where available*])
- Diaphragm (always used with spermicide [*where available*])

Acceptable forms of secondary contraception, when used with a barrier method, include the following:

- Combination hormonal contraceptives, hormonal patch, subcutaneous hormonal implant, or hormonal intramuscular contraceptives (medroxyprogesterone acetate depot)

Combination hormonal contraceptives, hormonal patch, and subcutaneous hormonal implant are not considered acceptable in the EU and some countries that follow the EU prescribing information for vismodegib.

Appendix 2 Definition of Women of Childbearing Potential and Acceptable and Unacceptable Forms of Contraception (cont.)

- Tubal sterilization

Other acceptable forms include the following:

- 100% commitment to abstinence from sexual intercourse (for medical or personal reasons)

Unacceptable contraception

The following are unacceptable forms of contraception:

- IUD progesterone T
- Progestin-only contraceptives
- Female condom

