#### Programming Note:

1. N is Number of Patients present in each *Disease Status* category i.e. Locally Advanced or Metastatic.
2. The variable *Baseline Age (varname BAGE)* should be used for Age information (in Age (years) and Age group (years) section). Baseline Age is the Patient's age (years)

at the informed consent (to study) date and it is derived from Informed consent date and Imputed Birth date (ASL.BAGE):  
(Set to integer part of (Informed consent date – Imputed Birth Date +1)/365.25).

If Birth date of subject is partial (at least year of Birth date is present) then use the following Missing Data Handling Rule:

- If the day part of the birth date is missing, impute it with 15.
  - If the month part of the birth date is missing, impute it with June.
- Age categories should be derived on the basis of Baseline Age.

3. Sex, Height, Weight, and Temperature information come from the Demography and Vital Signs CRF page. BMI is derived using the common formula defined in the DAP M3.

4. Race information comes from the Demography CRF page and as per SDTM controlled terminology

“Black” should be mapped as “Black or African American”.

Race was recorded as “Not applicable” in France.

5. Years from First BCC Diagnosis to Dose should derived as difference between First Treatment start Date and Date of First BCC Diagnosis comes from CRF page divided by year i.e. 365.25 days.

If First BCC Diagnosis date is partial then

a) Impute to the first day of the month if the day is missing.

b) Impute to the first month of the year if the month is missing.

6. Baseline ECOG Performance Status, Gorlin Syndrome, Child Bearing Potential information comes from CRF.

7. Number of Target Lesion at Baseline should be calculated as total number of target Lesions collected on last Tumor assessment date which is on or prior to First Dosing date having non missing Tumor Location and Tumor assessment date.

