## Adverse Events:

### General AE Reporting

Listings will include all AEs unless otherwise specified. A Treatment Emergent AE (TEAE) is defined as an AE that starts on or after the first day of study treatment and within 30 days of last dose (please see General Considerations for definition). Unless otherwise specified, AE and SAE summary tables will be restricted to TEAEs.

In STEVIE, the data collection guidelines require that the same AE is entered multiple times into the database, with a separate record for each change in toxicity grade or Lower Level Term. AEs can be reported using this or a “collapsed” Adverse Events analysis dataset.

The Collapsed Adverse Events dataset is derived by combining records that can be reasonably considered to be referring to a single AE term but with changes in toxicity grade (or lower level term). Records from the original AE dataset are grouped, and each group is represented in the collapsed dataset by a single record. The groups are built up by “chaining” records from the original dataset as follows:

- if the Subject ID, System Organ Class and Preferred Term are the same, and
- either the periods defined by the two AEs’ start and end dates overlap, or the Start Date of the later AE is  $\leq 2$  days after the End Date of the earlier one.

In the single record representing the “collapsed” AE:

- Subject ID, System Organ Class and Preferred Term are copied across from any of the records in the group (these are identical so it doesn’t matter which record these variables come from)
- Severity (i.e. toxicity grade) is taken as the most severe grade in the group
- Start Date is taken as the earliest start date in the group
- End Date, Lower Level Term and Outcome are taken from the record with the latest end date in the group

Examples are given on the next page.

Example of derivation of “collapsed” AEs:

Example 1:

SUBJID	System Organ Class	Preferred Term	Lower Level Term	Severity	Outcome	Start Date	End Date
	GASTROINTESTINAL DISORDERS	DYSPEPSI	DYSPEPSIA	GRADE 2 / MODERATE	RESOLVED		
	GASTROINTESTINAL DISORDERS	DYSPEPSI A	HEART BURN	GRADE 3 / SEVERE	RESOLVED		

Collapsed to:

	GASTROINTESTINAL DISORDERS	DYSPEPSI A	HEART BURN	GRADE 3 / SEVERE	RESOLVED		
--	----------------------------	------------	------------	------------------	----------	--	--

Example 2:

SUBJID	System Organ Class	Preferred Term	Lower Level Term	Severity	Outcome	Start Date	End Date

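### The amenorrhea denominator admits unflagged women only if they had the event, so the combined incidence sits at or above the true at-risk rate

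*SAP*

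**What the plan says.** The Additional Note in the SAP's Adverse Events section bases amenorrhea summaries on "the sub-population of patients who are at risk of this AE, including women of child-bearing potential or having menses at baseline". It explains that the demography page holds the childbearing flag but that "there is nowhere to indicate whether patients have menses", and draws the consequence: "so all patients who experienced the AE of interest (Amenorrhea/ Irregular Menses) were also included in the denominator".

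Four other places bear on the rule:

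- SAP, General AE Reporting: unless a table says otherwise, "AE and SAE summary tables will be restricted to TEAEs", that is, events starting from the first day of treatment up to 30 days after the last dose.
- SAP, programming note to the demographic table: "Baseline ECOG Performance Status, Gorlin Syndrome, Child Bearing Potential information comes from CRF". The flag is summarised there with the baseline characteristics.
- Protocol Appendix 2 lists what makes a woman of non-childbearing potential (age 50 or over with a year of natural amenorrhea, confirmed premature ovarian failure, bilateral salpingo-oophorectomy or hysterectomy, certain genetic or anatomical conditions) and then states: "Female patients who do not meet at least one of the above criteria are defined as women of childbearing potential".
- Protocol Table 1 has a row "Record Date of Last Menses", which footnote 11 limits: "In women of childbearing potential ONLY".

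Neither document gives the number of women, of flagged women, or of amenorrhea events, and the SAP text available shows no version of the rate with a denominator fixed at baseline.

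**The concern.** A denominator for an incidence should be settled before the outcome is known. Here one part of it is (the flagged women) and one part is not. An unflagged woman who menstruated at baseline belongs to the SAP's own target group whether or not she later has amenorrhea, yet she is counted only if she does. Each woman added this way brings one case and one patient at risk, and her event-free counterparts are absent.

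The figure carries some weight. Safety is the primary objective, adverse events are primary variables (Protocol 8.1.1), and amenorrhea or irregular menses triggers its own hormone tests and gynecological ultrasound (Protocol 5.3.2 and 5.3.13). There is no comparator arm, so the absolute percentage is the result. SAP outputs are also split by disease status, and the metastatic column holds only 96 patients of both sexes (Summary of Deaths mock-up). In a column that small, one or two added cases would show.

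**Working it through.** The plan states no amenorrhea count or rate, so there is no figure to reproduce. The direction follows from the rule; the size can only be illustrated.

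**Notation**

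- W = women flagged as of childbearing potential (demography CRF).
- a = flagged women with a treatment-emergent event.
- M = unflagged women with menses at baseline (not captured).
- b = unflagged women with a treatment-emergent event. If they belong to the target group, b ≤ M.

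**Three rates**

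- SAP rule: R = (a + b)/(W + b)
- Flagged women only: F = a/W
- The SAP's full target group: T = (a + b)/(W + M)

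**Direction**

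- Against T: the numerators are equal and W + b ≤ W + M, so R ≥ T, with strict excess when M > b and there is at least one event.
- Against F: R − F = b(W − a)/[W(W + b)] ≥ 0. This is zero when b = 0 and positive when b > 0, unless every flagged woman had the event.

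Enumerating W = 1 to 40, a = 0 to W, M = 0 to 20 and b = 0 to M gives 198,660 combinations. R was below F or T in none of them and above at least one of them in 196,200.

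**Size, with assumed counts (W = 100, a = 20, so F = 20.0%)**

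| b | R |
|---|---|
| 0 | 20/100 = 20.0% |
| 1 | 21/101 = 20.8% |
| 3 | 23/103 = 22.3% |
| 5 | 25/105 = 23.8% |
| 10 | 30/110 = 27.3% |

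Suppose unflagged menstruating women have the same 20% risk and b = 5. Then M = 25 and T = 25/125 = 20.0%, against 23.8% under the rule. The gap is the 20 event-free women who were never admitted.

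Over W = 50 to 150 and F = 10% to 30%, R − F is 0 for b = 0, 0.5 to 1.8 percentage points for b = 1, 2.3 to 8.2 for b = 5, and 4.4 to 15.0 for b = 10.

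**Source of the bias.** Enlarging the denominator is not what raises the rate: with the numerator held at a + b, dividing by W alone would give a higher figure still. The bias comes from adding cases to both parts without the matching non-cases.

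**The case against.** **The rule is disclosed, the analysis is descriptive, and the rate can be rebuilt.** The SAP states the rule and its reason, and Protocol 8.2 plans no hypothesis test. The childbearing flag appears by patient in the demographic listing and every event by patient in the adverse event listing, so someone holding both could recover F. All of this stands, but disclosure does not remove the bias, and a reader of the summary table alone sees only R.

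**The affected group should be nearly empty.** Under Appendix 2, women of non-childbearing potential would mostly not menstruate, so b would largely reflect miscoded flags. This stands as to size. It does not make b zero. The SAP note itself treats menses at baseline as something beyond the flag. The Protocol is also not uniform: inclusion criterion 14 treats surgical sterility as non-childbearing without naming the procedure, while footnote 12 of Table 1 keeps women with tubal ligation in the tested group. A site could therefore leave a menstruating woman with a ligation unflagged.

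**A baseline-only rate leaves out real events.** An unflagged woman with amenorrhea presumably had menses to lose. This is a fair cost, and the reason her event must still be reported separately.

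**A reader might infer that the rule pushes every row upward.** It does not, when the comparison is with the flag-only rate. The note adds patients with either amenorrhea or irregular menses and states no treatment-emergent limit, whereas tables are by preferred term and restricted to treatment-emergent events. If three unflagged patients had irregular menses only, an amenorrhea row of 20/100 = 20.0% would become 20/103 = 19.4%. Even that row cannot fall below the rate in the full target group, where the denominator is at least 103. The upward statement is therefore confined to the combined rate.

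**A reader might also infer that the last-menses row in Protocol Table 1 contradicts the SAP's statement that menses status is recorded nowhere.** The documents do not support this. Footnote 11 restricts that row to women of childbearing potential, and Protocol 5.3.8 and 5.3.10 do the same. The SAP's gap concerns women outside the flag, for whom no menses date is scheduled. The field cannot identify them.

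**Conclusion.** The point holds. Entry to the denominator depends on the outcome, and the combined amenorrhea/irregular menses incidence is at or above the true at-risk rate. Relative to flagged women only, it is inflated whenever a treatment-emergent event occurs in an unflagged woman and unchanged if none does.

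The size is unknown. It is probably small if sites applied Appendix 2 as written, and could reach several percentage points if even five events fell outside the flag. Every count used to show this is an assumption.

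The conclusion on direction rests on two conditions: unflagged patients with the event belong to the SAP's target group (so b ≤ M), and the events of added patients count in the numerator for the comparison with the flag-only rate. Correction is worthwhile because safety is the primary objective, the trial has no comparator, and the data needed are already collected.

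**What to change.** Define the amenorrhea denominator from baseline data only: women flagged as of childbearing potential on the demography CRF. Count treatment-emergent amenorrhea/irregular menses in that same set. Report the number of events in unflagged women in a footnote or listing so that none is lost. If the current rate is kept, show it only as a secondary figure beside the baseline-only rate.

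The cost is one derivation change and a footnote, with no new data. The downside is that a few events leave the percentage, and the rate then describes flagged women rather than every woman who menstruated at baseline; the table title should say so.
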